### 13.4 Vital signs

Vital signs (height (at baseline only), weight, blood pressure and heart rate) will be presented as absolute and change from baseline values over time by descriptive statistics. Individual absolute values for weight, blood pressure and heart rate over time will also be plotted.

# 13.5 Physical examination

A general physical examination will be assessed at Day 1/Baseline and at all visits until the Week 12 visit, and at the Study drug discontinuation visit if performed. Abnormal findings at Day 1 are reported and summarized under medical history and findings during the study are reported as AEs.

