6.5.5 Safety assessments

6.5.5.1 Adverse events

6.5.5.1.1 Definitions

Adverse event

An AE is any untoward medical occurrence in a patient or trial patient administered a pharmaceutical product; the event does not necessarily have a causal relationship with the treatment or usage.

Adverse events include the following:

- Abnormal test findings, as specified below.
- Clinically significant signs and symptoms.
- Changes in physical examination findings.
- Progression/worsening of underlying disease.

In addition, signs and symptoms resulting from the following should also be handled according to the same principles as Adverse Events:

- Overdose.
- Withdrawal of treatment.
- Interactions.
- Abuse.
- Misuse.

Abnormal test findings

An abnormal test finding, e.g. abnormal laboratory analysis results, vital signs or ECG, should be recorded as an Adverse Event in any of the following situations:

- The test is associated with accompanying symptoms. Note, that the symptom, not the test result, should be recorded as an AE.
- The test result leads to a medical/surgical intervention including withdrawal of IMP or discontinuation from the study. Repeat/confirmatory testing is not considered a medical intervention.
- The investigator considers the test result to be clinically significant.

Preexisting conditions

A preexisting condition (i.e., a disorder present before the adverse event reporting period started and noted on the pretreatment medical history/physical examination form) should not

be reported as an adverse event unless the condition worsens or episodes increase in frequency during the adverse event reporting period.

Worsening of Still's disease

A worsening of the disease under study should not be reported as an adverse event unless it leads to hospitalization or fulfills any other seriousness criterion.

Procedures

Diagnostic and therapeutic non-invasive and invasive procedures, such as surgery, should not be reported as adverse events. However, the medical condition for which the procedure was performed should be reported if it meets the definition of an adverse event. For example, an acute appendicitis that begins during the adverse event reporting period should be reported as the adverse event and the resulting appendectomy entered in the comments section of the CRF.

Serious adverse event (SAE)

An adverse event that meets one or more of the following criteria/outcomes is classified as serious:

- Results in death.

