6.5.5.3 Physical examination

A general physical examination will be assessed at Day 1 and at all visits until the Week 12 visit. It will also be assessed if the Study drug Discontinuation visit is performed. The assessment will be recorded as "normal" or "abnormal". Abnormalities should be specified.

At the Week 12 visit and at the Study Drug Discontinuation visit, if applicable, the presence or absence of specific physical examination findings which are associated with Still's disease such as rash, serositis, splenomegaly and generalized lymphadenopathy will be recorded to assess "inactive disease" (see 6.5.4.5).

Any persisting abnormalities should be stated each time the examination is performed. If any abnormalities are reported at baseline they should be recorded as medical history. New abnormalities reported after first dose of IMP should be recorded as AEs (see 6.5.5.1.1 for details).

The presence or absence of signs of joint inflammation will not be reported as AEs (see 6.5.5.1.1 Preexisting conditions/Worsening of Still's disease) but will be captured in joint assessment as part of ACR.

Any occurrence of rash will be recorded on a daily basis by the patient in the diary and as part of the physical examination assessment performed at the visits (see 6.5.4.4). If not judged to be attributable to the disease it should be recorded as an AE.

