8.3.7.4 Physical examination

The number and percentage of patients with presence of physical examination findings will be presented over time.

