Appendix 2 Guidance for MAS diagnosis

Characteristic clinical features of macrophage activation syndrome (MAS) are high non-remitting fever, hepatosplenomegaly, generalized lymphadenopathy, central nervous system dysfunction, and hemorrhagic manifestations. Typical laboratory abnormalities include pancytopenia, increased levels of ferritin, liver enzymes, lactate dehydrogenase, triglycerides, D-dimers, and soluble CD25 (sCD25), and decreased fibrinogen level. A typical histopathologic feature of MAS is the accumulation of well-differentiated macrophages exhibiting hemophagocytic activity in bone marrow biopsy specimen or aspirates (3, 56).

In patients <16 years old with systemic juvenile idiopathic arthritis the following laboratory classification criteria have been proposed (3), which can be used as a guidance, but the diagnosis of MAS will be made by the investigator based on the patients overall clinical signs and symptoms, including laboratory changes over time.

2016 Classification of macrophage activation syndrome in systemic juvenile idiopathic arthritis (3)

A febrile patient with known or suspected systemic juvenile idiopathic arthritis is classified as having macrophage activation syndrome if the following criteria is met:

- Ferritin >684 ng/ml

and any 2 of the following:

- Platelet count $\leq 181 \times 10^9$ /liter
- Aspartate aminotransferase >48 units/liter
- Triglycerides >156 mg/dl
- Fibrinogen ≤ 360 mg/dl

Laboratory abnormalities *should not be otherwise explained by the patient's condition*, such as, for example, concomitant immune-mediated thrombocytopenia, infectious hepatitis, visceral leishmaniasis, or familial hyperlipidemia.

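### SAP 13.5 omits the protocol's display of examination findings and relies on AE reporting, but conflicting protocol rules mean some Still's-related signs may reach no safety output

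*SAP*

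**What the plan says.** Among the safety analyses, Protocol 8.3.7.4 commits to an examination display: "The number and percentage of patients with presence of physical examination findings will be presented over time". SAP 13.5 describes when the examination is done and then says: "Abnormal findings at Day 1 are reported and summarized under medical history and findings during the study are reported as AEs". It specifies no output of its own.

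The protocol's rules on what becomes an AE point in two directions. Section 6.5.5.1.1 includes among AEs both "Changes in physical examination findings" and "Progression/worsening of underlying disease". Later in the same section comes: "A worsening of the disease under study should not be reported as an adverse event unless it leads to hospitalization", with the further proviso that any other seriousness criterion also triggers reporting. Section 6.5.5.3, on the examination itself, says: "New abnormalities reported after first dose of IMP should be recorded as AEs", and refers back to 6.5.5.1.1 for details. It then takes joint inflammation out of AE reporting and makes rash an AE only when it is not put down to the disease. It also asks that persisting abnormalities be restated at each examination.

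Appendix 5, footnote 5, requires hepatomegaly, splenomegaly, serositis, rash and generalized lymph-node enlargement to be specifically recorded at Week 12 and at the Study Drug Discontinuation visit.

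**The concern.** An output that the protocol promised is missing, and the only substitute is a statement about AE reporting that the protocol does not fully support. Two sites acting in good faith could treat the same new, non-serious, disease-attributed splenomegaly differently: one enters an AE, the other enters nothing on the AE page. The SAP has no rule for this, and where nothing is entered the finding has no place in the safety tables.

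The signs are relevant to safety. Appendix 2 opens its MAS guidance with: "Characteristic clinical features of macrophage activation syndrome (MAS) are high non-remitting fever, hepatosplenomegaly, generalized lymphadenopathy". MAS is the trial's event of special interest. The opposite site practice also has a cost: where non-serious disease worsening is entered as an AE, the TEAE tables mix disease activity with drug safety and nothing separates the two.

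**Working it through.** The plan gives no figure to reproduce. The check is to follow each type of on-study finding through the protocol's AE rules and then through the SAP's outputs.

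| Finding after first dose | Route to the AE tables | Other SAP output |
|---|---|---|
| Joint inflammation | None (6.5.5.3) | ACR components, SAP 12.2 |
| Rash attributed to Still's disease | None, by implication of 6.5.5.3 | Absence of rash by visit, SAP 12.4.2 |
| New sign not attributed to Still's disease | AE | TEAE tables, SAP 13.2 |
| Any sign meeting a seriousness criterion | SAE | SAE table and listing, SAP 13.2.1 |
| Diagnosed MAS | Always an SAE (6.5.5.1.1) | Patient count, SAP 13.2 |
| New non-serious splenomegaly, lymphadenopathy or serositis attributed to Still's disease | AE under 6.5.5.3 and two bullets of 6.5.5.1.1; not an AE under the worsening paragraph of 6.5.5.1.1 | Only inside the inactive-disease composite at Week 12 (SAP 8.5.4, 12.4.3) |
| Baseline finding that persists unchanged or resolves | None (pre-existing conditions, 6.5.5.1.1) | Baseline medical history only, SAP 10.4 |
| Hepatomegaly item recorded at Week 12 and discontinuation | As for other new signs | None; not part of the composite |

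From this:

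1. The first two rows show that the SAP sentence is not literally correct, but those findings are displayed elsewhere. Rows three to five are covered.
2. Row six depends on the site. The composite does not rescue these signs: SAP 12.4.2 and 12.4.3 present only how many patients have inactive disease at Week 12, without the components. In SAP Table 1 the Week 12 window starts at Day 72, so signs recorded at a discontinuation visit on or before Day 71 do not enter that count.
3. The last two rows do not depend on how a site reads the AE rule. The course of baseline findings is collected at each visit and shown nowhere. The hepatomegaly item is collected and given no use.

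Upper limit on what is undisplayed: post-baseline examinations are scheduled at Weeks 1, 2, 4, 8 and 12, so 5 per patient. SAP 4.2 expects at least 12 patients, giving 12 × 5 = 60 scheduled examinations at that number. This assumes that nobody discontinues, and it counts examinations, not abnormal findings. With 2:1 allocation the arms are 12 × 2/3 = 8 and 12 × 1/3 = 4, so one patient is 1/8 = 12.5% of the anakinra arm or 1/4 = 25% of placebo.

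**The case against.** The strongest reply is that SAP 13.5 largely restates Protocol 6.5.5.3, the section specific to examinations, which sends new abnormalities to AE reporting. Splenomegaly, lymphadenopathy and serositis have no express exemption there. A site following that section would enter them, and they would appear in the TEAE tables. This stands: a reader might infer that the protocol bars these signs from AE reporting and that they are certain to be lost, but the text is conflicting and does not support that.

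Second, a reader might infer that a difference between arms in MAS would go unseen. It would not. Diagnosed MAS is an SAE, goes to a blinded adjudication committee (Protocol 3.4) and is counted. The laboratory items in the Appendix 2 criteria are measured centrally and shown over time and in shift tables (SAP 13.3). Symptomatic serositis is an escape criterion, so it can surface indirectly among discontinuation reasons (SAP 9).

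Third, SAP 13.5 gives no reason for the missing display. That AE reporting was the reason is only an inference from the adjacent sentence. Other outputs were cut for small numbers, and this may be one of them. However, the SAP's small-sample statements concern dose groups, strata, centers and subgroups; laboratory and vital-sign displays were kept. SAP 8.1 describes what listings will contain but commits to none for the examination.

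Fourth, a percentage table by arm and visit says little with about 8 and 4 patients. That is fair, and it favors a listing.

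**Conclusion.** The point holds in a limited form. The SAP omits an output planned in the protocol, and its stated route for on-study findings has exceptions. New, non-serious signs attributed to Still's disease may be absent from the safety output, depending on site practice. The course of baseline findings and the recorded hepatomegaly have no specified output in any case.

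The number of findings affected cannot be derived; 60 examinations is a ceiling at 12 patients. A reader might try to size a distortion of AE rates from the planned response rates of 65% and 25%. The documents do not support this: they give no fraction of non-responders with a recordable worsening, and Protocol 8.3.4 separates non-response from worsening. That AE counts would favor anakinra is a possibility if placebo patients flare more and sites enter flares as AEs; it is not a result.

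The conclusion rests on the SAP text being complete as to outputs. No formal test depends on it. It is a modest gap in safety reporting that is cheap to close.

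**What to change.** - In SAP 13.5, restore the output of Protocol 8.3.7.4. With about 12 patients, a patient listing by arm and visit is enough; a by-visit table is the alternative. Include the Study Drug Discontinuation visit and the specifically recorded signs: hepatomegaly, splenomegaly, serositis, rash and lymph-node enlargement.
- Reword the SAP sentence so that it no longer says that all on-study findings are AEs, and name the exceptions.
- Reconcile Protocol 6.5.5.1.1 and 6.5.5.3 with SAP 13.5, so that one rule covers non-serious signs attributed to Still's disease.
- In the TEAE tables of SAP 13.2, put any Still's-worsening terms on a separate line.

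The cost is one listing or table and a few wording changes, with no new data. SAP 5.2 has the SAP finalized before database lock, so the output can be specified before unblinding. The limit is that wording changes cannot alter AE data already recorded; the listing and the separate TEAE line are what make differing site practice visible.

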# 14 Pharmacokinetic analyses

Anakinra trough concentrations will be derived from the serum concentration data, and will be summarized at each visit with descriptive statistics.

Repeated-dose PK at Week 12 will be presented using individual patient concentration-time plots on the semi-log and linear scales. Calculated PK parameters at Week 12 will be listed.

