There is limited information about the PK of anakinra in SJIA patients, and no information about the PK of anakinra in AOSD patients. The PK of anakinra is however well characterized in healthy volunteers and RA patients. The bioavailability is high (~95%), t_{max} is about 6 hours and anakinra serum concentrations decline with a half-life of 4-6 hours following s.c. administration to RA patients. The exposure increases in approximate proportion to dose, accumulation is modest following once daily administration and approximately 80% of anakinra is eliminated by the kidney. In JIA patients trough anakinra concentrations were lower in the age group 3-6 years compared to older children and in 22 SJIA patients clearance was higher in children with a lower body-weight (28).

For a detailed description of anakinra characteristics, contraindications, warnings and precautions, adverse reactions and pharmaceutical properties, refer to the product information/monograph and the IB.

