6.5.6.1.1 Repeated-dose pharmacokinetics (pre-selected PK sites)

The repeated-dose PK of anakinra will be evaluated at 2 mg/kg/day (max 100 mg/day) and 4 mg/kg/day (max 200 mg/day). The planned target per dose level is 5 patients with disease onset <6 years, 5 patients with disease onset ≥ 6 to <16 years and 5 patients with a disease onset ≥ 16 years.

At the Week 12 visit, the IMP dose will be administered at the site and blood samples will be collected before the IMP administration and at 2, 4, 6 and 8 hours after IMP administration. The visit will be scheduled so that the IMP dose will be administered 24 hours (acceptance range 22-30 hours) after previous IMP dose the day before.

If exceeding maximum allowed blood volume for any patient, the samples at 4 and 6 hours may be replaced by a sample at 5 hours.

See Appendix 6 for a detailed description of the PK sampling procedure.

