8.3.8 Analysis of pharmacokinetics

The PK variables will be presented by descriptive statistics by dose and age group.

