# 8 General issues for statistical analysis

The comparison of interest is between anakinra (2 mg/kg and 4 mg/kg combined) and placebo. Due to the small number of patients in the individual dose groups of anakinra, summary tables (except for the drug exposure summary) will not provide results by individual dose groups. Likewise, the randomization was stratified by age at onset of disease (< 16 years,  $\geq$  16 years) and glucocorticoid use (yes, no), but due to the very small number of patients for levels of the stratification factors within each treatment group, descriptive statistics and statistical analyses will generally not be performed by stratification factors. For primary and key secondary efficacy endpoints, dose-level information and stratification allocation will be included in a patient listing.

All statistical tests will be two-sided and performed using a 5 % significance level, if not stated otherwise. Results will be presented as the estimated value for each treatment group, anakinra and placebo, the estimated difference between groups, the associated 95 % two-sided confidence interval and p-value. P-values from statistical analyses will be presented to three decimal places with values below 0.001 displayed as <0.001 and 95 % confidence intervals will be presented to one more decimal place than the raw data.

Continuous data will be summarized using descriptive statistics: n, mean, SD, median, minimum and maximum, unless otherwise indicated. Minimum and maximum will be presented to the same number of decimal places as the raw data and mean, SD, and median will be presented to one more decimal place than the raw data.

Categorical data will be summarized using counts and percentages. Percentages will be suppressed when the count is zero, however the category will still be displayed. The denominator for all percentages will be the number of patients within the treatment group for the population of interest, unless otherwise indicated. Percentages will be presented to one decimal place.

Statistical analyses will be performed using SAS software Version 9.4 (SAS Institute Inc, Cary, North Carolina, United States).

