#### **8.1** Time windows

For the purpose of the statistical analysis and if not otherwise specified, all the variables (primary, secondary and exploratory variables) will be assigned to the visit/assessment timepoint in which they were collected depending on the following analysis time windows in Table 1.

Table 1 Time windows

Visit	Week	Study Day	Study Day window
1	Baseline	1	≤1
2	1	8	2-11
3	2	15	12-22
4	4	29	23-43
5	8	57	44-71
6	12	85	≥ 72

Unscheduled visit data will be considered when assigning assessments to the analysis visit. If more than one assessment of the variable (scheduled or unscheduled) falls in the same time window but on different days, the closest to the scheduled visit day will be taken, or the earlier, in the event the values are equidistant from the nominal visit date. If several measurements are collected during the selected day, the average (for numeric values)/worst (for categorical values) of the measurements will be taken.

In summaries of extreme values as opposed to visit-based summaries, all post baseline values collected are used including those collected at unscheduled visits regardless if the value is closest to the scheduled visit date or not. For summaries at a patient level, all values should be included, regardless of whether they appear in a corresponding visit-based summary, when deriving a patient level statistic such as a maximum.

Listings will display all values contributing to a time point for a patient.

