## 13 Safety analyses

### **13.1** Treatment exposure

Exposure to study drug (prescribed daily dose, actual daily dose received and duration of treatment) will be summarized by dose group (2 and 4 mg/kg/day) with descriptive statistics.

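### Read together, SAP 8 and SAP 14 pool trough concentrations across 2 and 4 mg/kg/day, so the summary cannot be read against either dose

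*SAP*

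**What the plan says.** The pooling comes from two SAP sections read together; neither states it alone.

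- SAP 14: "Anakinra trough concentrations will be derived from the serum concentration data, and will be summarized at each visit with descriptive statistics". No split by dose is mentioned. The Week 12 repeated-dose profiles are plotted per patient and their parameters are listed, so they are not affected.
- SAP 8, citing small dose groups: "summary tables (except for the drug exposure summary) will not provide results by individual dose groups". The exception is SAP 13.1, which covers the dose prescribed, the dose received and treatment duration. It does not cover serum concentrations.
- SAP 8, on listings: "For primary and key secondary efficacy endpoints, dose-level information and stratification allocation will be included in a patient listing". Pharmacokinetic data are not mentioned.
- SAP 7.3 limits the PK set to patients who received anakinra. The mixing is therefore between the two doses, not with placebo.
- Protocol 4.1: "The exposure increases in approximate proportion to dose".
- Protocol 6.2.1, Table 2, gives predicted steady-state exposure at both doses for three body weights.
- Protocol 8.3.8: "The PK variables will be presented by descriptive statistics by dose and age group".
- SAP 8.1 assigns results to visits by study-day window. Unless something else is specified, "all the variables (primary, secondary and exploratory variables) will be assigned to the visit/assessment timepoint" according to those windows.

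**The concern.** Small numbers are a fair reason to combine the doses when anakinra is compared with placebo. They are a weaker reason to average concentrations from two regimens that the protocol itself expects to differ about two-fold. The resulting mean and SD would describe a mixture whose composition depends on who is still contributing samples at that visit. A reader could not compare the result with Table 2 or with any other dose-specific figure. A change between visits could also reflect a change in dose mix and not in pharmacokinetics.

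A smaller matter is that SAP 14 does not say which samples qualify as troughs. Under Protocol 6.3.3 and 6.5.1.9, serum is taken at the Study Drug Discontinuation visit, and patients who stop before Week 2 are still asked to attend Week 2. A sample from such a Week 2 visit falls in the Week 2 window although the patient may have been off drug for days.

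**Working it through.** **1. Inputs.** Predicted minimum concentration (Cmin, ng/mL) from Protocol Table 2. Daily doses in mg are from Protocol Appendix 3.

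| Body weight | 2 mg/kg/day | 4 mg/kg/day | Ratio |
|---|---|---|---|
| 20 kg | 95 (40 mg) | 191 (80 mg) | 2.01 |
| 50 kg | 236 (100 mg) | 472 (200 mg) | 2.00 |
| 100 kg | 212 (100 mg) | 424 (200 mg) | 2.00 |

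The AUC ratios are 23121/11561, 37552/18776 and 27111/13556, all 2.00. The 2.01 is rounding: unrounded values consistent with 95 and 191 give ratios from 1.99 to 2.03. The predicted doubling is confirmed at each weight.

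The absolute values in Table 2 do not follow from its footnote as printed. At 20 kg, CL/F = 0.847 × (20/70)^0.47 gives an AUC of 85092 ng·h/mL for 40 mg, against 11561 in the table. This may be an artefact of text extraction. The ratio of 2 does not depend on it, because it holds in any linear model.

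**2. Expected numbers.** SAP 4.2 expects at least 12 randomized patients at 2:1, so about 8 on anakinra. The 1:1:2:2 ratio gives about 4 per dose.

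**3. Pooled mean at one body weight.** With 4 + 4 patients the pooled mean is (C2 + C4)/2, where C4 = 2 × C2. That equals 1.5 × C2, or 0.75 × C4.

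- 20 kg: (95 + 191)/2 = 143
- 50 kg: (236 + 472)/2 = 354
- 100 kg: (212 + 424)/2 = 318

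At 50 kg every patient lies 118 from the pooled mean, so dose alone contributes an SD of √(8 × 118²/7) = 126 ng/mL.

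**4. Sensitivity to dose mix.** With n4 of 8 patients on 4 mg/kg, the pooled mean divided by C2 is 1 + n4/8.

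| 2 mg/kg : 4 mg/kg | Pooled / 2 mg/kg value | Pooled / 4 mg/kg value |
|---|---|---|
| 2:6 | 1.75 | 0.88 |
| 4:4 | 1.50 | 0.75 |
| 6:2 | 1.25 | 0.63 |

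**5. Body weight.** From 20 to 50 kg, Cmin rises by 236/95 = 2.48 at the lower dose and 472/191 = 2.47 at the higher, which is more than the dose effect. The three Table 2 values at 2 mg/kg have mean 181 (SD 75), those at 4 mg/kg have mean 362 (SD 150), and all six have mean 272 (SD 146). A split by dose separates the two means but does not remove the spread due to weight.

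**6. Dose-normalised form.** Cmin divided by the daily dose in mg gives:

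- 20 kg: 95/40 = 2.38 and 191/80 = 2.39
- 50 kg: 236/100 = 2.36 and 472/200 = 2.36
- 100 kg: 212/100 = 2.12 and 424/200 = 2.12

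The six predictions then span 2.12 to 2.39 ng/mL per mg, a factor of 1.13. Before normalising they span 95 to 472, a factor of 5.0.

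**The case against.** The pooling is disclosed and reasoned, it concerns a descriptive endpoint, and the groups are tiny. Several further objections have force.

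- **Protocol plan.** A reader might infer from Protocol 8.3.8 that troughs by dose were explicitly planned and then dropped. The text does not support that. Protocol 6.5.6.3.1 defines the PK variables as the non-compartmental set (such as Cmax, AUC and CL/F), and the endpoint definition names troughs separately from the repeated-dose parameters. The point rests on Table 2 and the stated dose proportionality.
- **Weight.** Weight matters as much as dose: 4 mg/kg at 20 kg (191) is predicted below 2 mg/kg at 50 kg (236). This stands, and a by-dose table alone is not enough.
- **Individual data.** SAP 8.1 promises listings of all values contributing to a time point. This helps, but dose labels are required only in the efficacy listings.
- **Population analysis.** Protocol 6.5.6.3.2 would use all concentrations with dose and weight as covariates. SAP 17.1.1 makes that analysis optional, so it is partial cover.
- **Off-drug samples.** It is tempting to say that discontinuation-visit samples are not troughs. That is too strong. When drug is stopped at a scheduled visit, the discontinuation visit replaces it, and such visits are timed about 24 hours after the last dose, so the sample can be a valid trough. The documents do not say that off-drug samples will be counted, and they give no basis for estimating how many there would be. Only the selection rule is missing.
- **Measured values.** The assay (Protocol 6.5.6.2) detects endogenous IL-1Ra as well as anakinra, so measured troughs need not double exactly.

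**Conclusion.** The concern holds for the pooling. Followed as written, the SAP yields a trough summary per visit that mixes two regimens predicted to differ two-fold at a given body weight. With equal numbers at one weight, the mean is 1.5 times one dose's value and 0.75 times the other's. Dose splits from 2:6 to 6:2 move it between 1.75 and 1.25 times the 2 mg/kg value.

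These sizes assume the linear predictions of Table 2, equal body weight across doses and about 8 patients on anakinra. Real body weights will vary and will add spread of similar size, so the figures illustrate the problem and do not forecast the result.

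The rule for selecting trough samples is unstated and needs clarifying, but that is secondary. No hypothesis test or efficacy conclusion is affected.

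**What to change.** Add an explicit exemption for SAP 14 to the dose-group rule in SAP 8. Then:

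1. Summarise troughs at each visit by dose level with n, median, minimum and maximum. If a single summary is preferred, use concentration divided by the daily dose in mg.
2. Add a per-patient listing or plot showing dose level, body weight and time since last dose. With about four patients per dose, this carries most of the information.
3. Define a trough as a pre-dose sample from a patient still on study drug, or a sample taken about one dosing interval after the last dose. This keeps discontinuation-visit samples drawn about 24 hours after dosing and leaves out later ones.

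The cost is SAP wording and table layout. Protocol 6.5.6 already requires dosing and sampling times to be recorded, so no new data are needed. The drawback is that by-dose summaries rest on very few patients and should be presented as descriptive only.
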